H. Collaboration: This is a Multi-PI application from Drs. [name] and [name] from the University of Kansas Medical Center and East Carolina University, respectively. Both investigators have been conducting research on statins for several years. The project was born out of a common desire to combine their individual expertise to investigate the mechanisms underlying skeletal muscle complications associated with statin therapy in a repeated measures, longitudinal design. Due to the scope of the design (i.e., number of subjects, duration) and complexities of the primary outcome measures, it was felt a multi-PI, multi-institutional approach represented the most efficient and statistically valid means of completing the project and thereby making truly sustained impact of the field. Each investigator has trained at/frequently visited the other institute and is quite familiar with the research environments. Standard operating procedures will be developed for all common testing and primary outcome measurements, and each investigator and their key personnel will visit the other institute prior to commencing the study to conduct trial runs to insure continuity. The PIs will share responsibility for fiscal and research management. Using the multi-PI approach with two investigators with translational research experience and complimentary analytical expertise dramatically increases the power of the study and the likelihood of successfully completing the proposed aims.

I. Single IRB Review for a Multi-site study: NA

J. Personnel who will conduct the study, including:

1. Indicate, by title, who will be present during study procedure(s): PI, Study Coordinator
2. Primary responsibility for the following activities, for example:
 - a. Determining eligibility: PI, Study Coordinator
 - b. Obtaining informed consent: PI, Study Coordinator
 - c. Providing on-going information to the study sponsor and the IRB: PI, Study Coordinator
 - d. Maintaining participant's research records: PI, Study Coordinator
 - e. Completing physical examination: PI, CTSU Nurse
 - f. Taking vital signs, height, weight: CTSU Nurses
 - g. Drawing / collecting laboratory specimens: CTSU Nurses
 - h. Performing / conducting tests, procedures, interventions, questionnaires: PI, Study Coordinator
 - i. Completing study data forms: Study Coordinator
 - j. Managing study database: PI

K. Assessment of Subject Safety and Development of a Data and Safety Monitoring Plan

- a. Key personnel:** [name], [name], [name], [name], study physician at KUMC and [name], study physician at ECU.
- b. Plan for safety monitoring and review:** [name] will serve as the Chair of the Data Safety Monitoring Board and will convene every 6 months with the other members, Drs. [name] and [name] to make decisions on safety of the participants. Enrollment data will also be reviewed twice a year by the DSMB. In addition, data will be reviewed on a yearly basis with the biostatistician, [name] to determine if the studies should be shortened due to either no measured effect or due to effects that are greater than what power calculations indicated. If problems occur with participants, blinded study staff will alert [name]. [name] will have access to dose and type of statin and will consult the study physicians cardiologist to make a decision on whether the subject should be removed from the study for safety concerns. The PI and other key personnel will be examining research data on a subject to subject basis to ensure it is accurate and to address any potential problems that may arise with the protocols. In addition, Drs. [name] and [name] will discuss data at least once per month through in person meetings or by phone to ensure that data collection is occurring in a consistent manner at both locations.**Plan for adverse event reporting:** Adverse events will be defined as any untoward medical occurrence in study participants or others immediately involved in the performance of the protocol, which does not necessarily have a causal relationship with the study treatment, but results in a change in intervention, daily function, hospitalization or rated category 3 or above using the National Cancer Institute Common Terminology Criteria for Adverse Events (CTCAE) v3.0. Expected events such as slight muscle soreness consistent with statin therapy, or those consistent with a participant's prior medical history not sufficient to alter the intervention will not be considered an AE. Staff involved in performance of the protocol (e.g. coordinators) will continually monitor participants for adverse events throughout the intervention, and study staff will assess adverse events at every testing visit as well as during regularly scheduled telephone assessments with all randomized participants.
If study staff, tester, or participant reports adverse events or complaints, relevant information will be collected and documented. The participant will be evaluated by the unblinded investigator identified in the protocol. The investigator will determine the severity (according to the CTCAE) and relatedness of the AE to the intervention. The investigator will identify adverse events of clinical concern, those that may require further workup, or suggest that additional participation in the intervention might be a safety risk. These AEs will first be discussed with the participant and then communicated to the study staff or providers with participant's consent and as appropriate. Serious adverse events directly related to study intervention will be reported immediately to the IRB. Any adverse event rate over 30% in 12 mo will be reported to the NIH.

III. Subject Participation

A. Recruitment:

- a.** Subjects will be recruited from the KUMC campus, from hospitals and clinics associated with KUMC and metro-Kansas City, Kansas and Missouri areas. Recruiting will occur through physicians and clinics and through advertisements in emails, flyers, newspaper

ads, radio spots, etc. Interested subjects will call or email and undergo initial phone screening, conducted by trained study staff, to see if they qualify. Should they meet the initial qualifications, they will come to the lab for an informed consent meeting with the PI, research coordinator, or other study staff. They will then be provided with an informed consent that is fully approved by the IRB at KUMC to review prior to the in-person meeting. Subjects who are interested in taking part in the study will be asked to sign the informed consent in the presence of a witness. Participants will have adequate opportunity to review the informed consent and to ask any questions they may have about the research protocol, compensation, risks, and benefits of taking part in the study.

- b.** The targeted/ planned distribution of subjects by sex/gender and racial/ethnic groups for the proposed study or protocol will follow the local demographics. The Kansas City area has a population that is comprised of 13 % African American, 2% Asian, 5% Hispanic, and 80% Caucasian. It is anticipated that the study population at KUMC will have much the same racial and ethnic make-up. Statistical comparisons among minorities or between minority and Caucasian groups are not aims of the current study. We fully intend to enroll every eligible minority individual in these studies. Ample pools of all targeted populations exist.
- c.** Selection criteria: Only premenopausal women will be included in this study because of the possible complications that hormone replacement therapy may have upon findings. It is anticipated that women will comprise approximately 50% of the study subjects. It is also anticipated that gender will not be a significant factor in the response to exercise training or statin therapy, and hence, it is anticipated that the data from both genders will be compiled and analyzed as a group.
- d.** Exclusions: No minority groups will be excluded.
- e.** Outreach: The subject pool will be limited to the greater Kansas City (MO and KS) area. Subject will need to make regular visits to the laboratories, and thus, subjects will only be recruited who are within the county region and can regularly make appointments.

B. Screening Interview/questionnaire: NA

C. Informed consent process and timing of obtaining of consent: Should the participant meet the initial qualifications, they will come to the lab for an informed consent meeting with the PI, research coordinator, or other study staff. They will be provided with an informed consent that is fully approved by the IRB at KUMC to review prior to the in-person meeting. Subjects who are interested in taking part in the study will be asked to sign the informed consent in the presence of a witness. Participants will have adequate opportunity to review the informed consent and to ask any questions they may have about the research protocol, compensation, risks, and benefits of taking part in the study.

D. Alternatives to Participation: NA

E. Costs to Subjects: There is no cost to subjects for participation in this study.

F. How new information will be conveyed to the study subject and how it will be documented: New information about risks associated with involvement in the study will be disseminated but no other information will be disclosed.

G. Payment, including a prorated plan for payment: Participants will receive a one-time compensation of \$400 for completing all study visits. If participation ends early, participants will receive \$75 for each study visit excluding screening. They will be given a ClinCard, which works like a debit card. After completion of the study, payment will be added to the card by computer. The money will be available within 1 business day. Participants can use the ClinCard at an ATM or at a store. Study staff will collect their name, address, and social security number to allow them to set the participant up in the ClinCard system through the KUMC Research Institute. Study payments are taxable income. A form 1099 will be sent to the subject and the Internal Revenue Service if your payments are \$600 or more in a calendar year. The subjects' personal information will be kept on a secure computer. It will be removed from the computer after the study is over and the money on the card has been used. The information will not be shared with other businesses. It will be kept confidential.

H. Payment for a research-related injury: We will include the following text in the consent form: "All forms of medical findings, whether routine or experimental, involve some risk of injury. In spite of all safety measures, you might develop medical problems from participating in this study. You must report any suspected illness or injury to the study coordinator immediately. If such problems occur, you will be provided with emergency medical treatment and the investigator will assist you in getting proper follow-up medical treatment. Neither the investigator nor the sponsor will provide compensation for research-related injuries. Payment of lost wages, disability or discomfort is not available. You do not give up any of your rights by signing this form."

IV. Data Collection and Protection

A. Data Management and Security: All identifiable files, data, and tissue will be coded and stored in secure locations. These data include: study progression, subject numbers, percent completion, data quality, subject retention, adverse events, etc.

The PIs at both KUMC and ECU will be responsible for the quality of the data and will supervise the data acquisition with the help of study coordinators. All data will be coded for confidentiality, and only the PI, study coordinator, and study statistician will have access to the code. The results of each test on each subject will be screened by the study coordinator prior to entering on the spreadsheet. This is standard practice in our laboratories. Hard copies are kept in dedicated locked cabinets. Coded data files will be sent to the study statistician for statistical analyses. These analyses will be sent to the PI and study coordinator for dissemination to appropriate co-Is. At the end of participation in the study, each subject will receive a personal data summary of their test results. The study coordinator or a study investigator will discuss the results with the subject.

After 1 year, the PI's including the biostatistician, [name] He will be un-blinded but the study staff will remain blinded, so that the important research findings can begin to be

delineated. This will also allow for [name] to be able to examine if the trial is finding more or less significant effects for outcome measures.

- B. Sample / Specimen Collection:** All subjects will be assigned a data code. Blood and tissue samples will be labeled with the participant's data code and stored in a locked freezer. Blood and tissue samples will be stored indefinitely following completion of current project for future research.
- C. Tissue Banking Considerations:** Following completion of the current project, remaining blood and tissue samples will remain in locked freezer indefinitely. Samples will only be used by investigators of the current project, both KUMC and ECU, when a new biomarkers or techniques of interest emerge.
- D. Procedures to protect subject confidentiality:** Risks to confidentiality are reduced by assigning all subjects to a data code. Folders are stored in locked file cabinets, and only the PI and study coordinator have access to the locked files. Individual names or initials are not used in any discussions or publications of the data.
- E. Quality Assurance / Monitoring:** Data will be reviewed twice a year by the Board Chair. In addition, data will be reviewed on a yearly basis with the biostatistician, [name] to determine if the studies should be shortened due to either no measured effect or due to effects that are greater than what power calculations indicated. The PI and other key personnel will be examining research data on a subject to subject basis to ensure it is accurate and to address any potential problems that may arise with the protocols. In addition, Drs. [name] and [name] will discuss data at least once per month through in person meetings or by phone to ensure that data collection is occurring in a consistent manner at both locations.

V. Data Analysis and Reporting

- A. Statistical and Data Analysis:** This project is a two-factor study. One factor is treatment group (between subjects) and a second factor is time of data collection (0, 1, 6, and 12 months) (within subject). The data analysis will be carried out for the primary outcome variable of cardiorespiratory fitness, in addition to other outcome variables (muscle mitochondrial change, and insulin sensitivity, etc.). For each measure, its baseline measure and age will be added as covariates to adjust for the individual difference at baseline. Two-way interaction between treatment and time will be added in the model for testing if the outcome changes differently between groups over time. Additional variables, such as demographics, BMI, physical activity, etc. may also be included as covariates. If the test of trend difference is significant, then the comparison at each time point will also be considered to identify when the difference between groups reaches the maximum. Least Square Means will be used for the aforementioned comparisons. The statistical analysis will be performed with mixed procedure in STATA 13.1 (StataCorp LP, College Station, TX). Mixed model does

not require complete data for a longitudinal study. Residual analyses will be conducted and efforts to address those will be made, including appropriate transformations.

B. Expected Outcomes: The EX+Plac group and EX+Atorva20 groups will have a significant increase in VO₂peak, stroke volume, and a lowering of resting heart rate, common responses to exercise training. Measures of mitochondrial content (citrate synthase) and function (in-vivo NIRS, and ex-vivo respiration) will improve following the intervention, and will be preceded by increases in transcription factors (PGC-1 α , NRF-1, NRF-2, mTFA) known to control mitochondrial biogenesis measured at 1 month. Insulin sensitivity will also improve in the EX+Plac and Ex+Atorva20 groups. In contrast, the EX+Atorva80 group will display diminished mitochondrial and cardiorespiratory adaptations because of compromised respiratory capacity and disturbances in redox balance in skeletal muscle. This may occur due to a blunted exercise induced increase in PGC-1 α which is known to up regulate anti-ROS defense enzymes (101). Other cardiovascular adaptations may not improve in the EX+Atorva80 group, which could be due to impaired mitochondria oxygen consumption. We expect measures of pain and function to be triggered by the combination of exercise and Atorva80 treatment. These findings would indicate that higher dose atorvastatin impair exercise adaptations and that physicians should consider prescribing lower dose atorvastatin to patients who plan to utilize exercise training to lower cardiovascular risk. If these findings occur we will have remaining tissues to examine further mechanisms including if these findings are associated with reduced cellular ubiquinone levels, and altered balance between pathways controlling autophagy and apoptosis (Bcl-2 and Bax). These can be further supported by immunofluorescent examination of muscle fiber type changes and quantification of apoptosis by TUNEL staining. Given that a rodent study showed atorvastatin therapy blocked exercise induced increases in Glut4 mRNA and glycogen content (102), and that mitochondrial adaptations are critical for improved insulin sensitivity, we expect the EX+Atorva group will also display impaired improvements in insulin sensitivity.

C. Study results to participants: At the end of participation in the study, each subject will receive a personal data summary of their test results. The study coordinator or a study investigator will discuss the results with the subject. Results to be shared include: Body composition, exercise testing results, lipid profile, liver function (ALT), and glucose and insulin results from IVGTT, and summary of physical activity levels.

D. Publication Plan: We will publish all data derived from this award in a timely fashion and to make those data freely available to the general research community whenever possible. All genomic data will be made publicly available through NCBI's Gene Expression Omnibus (GEO), and all publications that result from this work will be deposited in PubMed Central (PMC).

VI. Bibliography / References / Literature Cited

1. Wilson TM, and Tanaka H. Meta-analysis of the age-associated decline in maximal aerobic capacity in men: relation to training status. Am J Physiol Heart Circ Physiol. 2000;278(3):H829-34.

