B. Study Type and Design: This study is a longitudinal, repeated measures, double-blinded design with subjects randomly assigned to placebo, low (20 mg/d) or high (80 mg/d) atorvastatin therapy during a 12-week aerobic exercise training protocol. We expect to screen approximately 150 participants to enroll (randomize) a maximum of 80 participants. The overall goal is to have 60 participants complete all study procedures (20 in each group). Repeated measures design allows each subject to serve as their own control. Placebo groups are included to account for potential changes in muscle mitochondrial function independent of statin therapy over the 1 year dose-response.

C. Sample size, statistical methods, and power calculation: The randomization for study drugs will be carried out by the biostatistician using a computer-based random number generator at a 1:1:1 allocation. Sample size for the study is powered on the basis of detecting a difference in VO₂peak between the EX+Plac group and the EX+Atorva80 group as well as between the EX+Atorva20 group and the EX+Atorva80 group at 12 weeks post-treatment. In our previously published study(13) (Table 2) the EX only group had a mean 2.6 ml/kg/min increase in VO₂peak following 12 weeks of training while the EX+Statin group only had a 0.4 ml/kg/min increase in VO₂peak. The estimated effect size of between group differences is 0.9 (Cohen's d). The increase of VO₂peak in the EX+Atorva20 group is expected

to be similar to that of EX+Plac group. A sample size of 35 per group provides 80% of power of detecting an effect size of 0.75 for a two-sided, two-sample t-test at 0.025 levels. Here, we use 0.025 for each group comparison to maintain the overall type I error rate at 0.05 level using Bonferroni correction. Assuming variances similar to what was observed in the pilot study, this study is powered to detect a difference of 1.53 ml/kg/min VO₂peak between groups. These power calculations led to a desired final sample size of 105 (35/group). We plan an enrollment of 120 (40/group) subjects to account for 10% dropout rate. The subject enrollment will be split equally between the two sites. As an exploratory analysis, the mean difference of VO₂peak (EX+ Atorva20- EX+ placebo) and its 95% confidence interval (CI) will be estimated. If the lower bound of the 95% confidence interval is greater than -0.8 ml/kg/min, EX+ Atorva20 will be considered non-inferior to EX+ placebo.

D. Subject Criteria

[figure not shown]

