- iv. Muscle biopsy: After an overnight fast, the participant will complete a survey to confirm the absence of bleeding disorders, and avoidance of NSAIDs and aspirins for 7 days prior to biopsy. Participants will then lie on a table in a supine position. A location on the mid-thigh will be identified. The area will be properly shaved and then thoroughly cleaned using sterile techniques (alcohol and iodine). A sterile drape is then placed over the leg with the biopsy site showing through a fenestration in the center of the drape. A numbing agent will be lightly sprayed onto the biopsy location (ethyl chloride) immediately before the skin, adipose, and muscle fascia is anesthetized with lidocaine (1-2% HCL). After allowing 1-2 minutes for the site to become numb the skin and fascia is incised with a sterile scalpel (#11). The Bergstrom needle (5mm) is then placed through the incision into the vastus lateralis muscle. Suction is applied to the proximal port of the needle, and the tissue is cut rapidly with the internal portion of the needle, and the entire needle is removed from the incision. Sterile gauze is placed on the incision site and pressure is applied with an ice pack for ~5 minutes. The site is then closed with a steri-strip and band-aid. Sterile gauze is then applied on top of the band-aid and pressure is applied by wrapping coban around the thigh. Approximately 100-200 mg of skeletal muscle will be collected during each biopsy in one pass. In the case where less muscle is harvested per pass, one more additional pass will be taken with the participants consent. The tissue collected is

dissected free of connective tissue and separated for mitochondrial function studies or frozen in liquid nitrogen for subsequent biochemical analyses as done previously (13, 61). After analysis for current project is complete any remaining muscle samples will be stored indefinitely for future research. Muscle biopsies will be repeated at 4 weeks and 12 weeks. [name] has performed over 300 skeletal muscle biopsies without incidence since starting his independent lab in 2005. See appendix for letter from IRB Director ([name]) at [name] previous institution (MU) stating his record for conducting muscle biopsies and a letter of support for the procedure from [name], the Director of the CTSU. Additionally, Neurologists who study various muscle diseases regularly perform the technique at KUMC. Muscle biopsies will be repeated at 4 and 12 weeks.

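### Sections II.B (at most 80 randomised, 60 completing) and II.C (120 enrolled, 105 final) give sample sizes that do not agree, whether II.B is read as the whole trial or as one site's share

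*Combined protocol and SAP*

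**What the plan says.** Section II.B expects about 150 people to be screened in order to "enroll (randomize) a maximum of 80 participants. The overall goal is to have 60 participants complete all study procedures (20 in each group").

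Section II.C, which follows directly, rests on a different size: "A sample size of 35 per group provides 80% of power of detecting an effect size of 0.75", using a two-sided two-sample t-test at 0.025 (Bonferroni for two comparisons: placebo versus 80 mg, and 20 mg versus 80 mg). It continues: "These power calculations led to a desired final sample size of 105 (35/group"), and "We plan an enrollment of 120 (40/group) subjects to account for 10% dropout rate". It then adds: "The subject enrollment will be split equally between the two sites". That last sentence fixes the scope of II.C: 120 is the total over two sites, and 105 is therefore trial-wide too. Section II.B contains no such sentence.

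On effect size, II.C reports from the earlier simvastatin study that "The estimated effect size of between group differences is 0.9" (increases of 2.6 and 0.4 ml/kg/min), and says that "this study is powered to detect a difference of 1.53 ml/kg/min".

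On location, section II.G places the whole study at KUMC. Sections II.H, II.K and IV.A describe investigators and data collection at both KUMC and East Carolina University (ECU).

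**The concern.** The number randomised is a basic design parameter, and the plan gives two values that cannot both hold for the same trial. A reader cannot tell how many participants will be randomised, how many will be analysed, what loss was planned for, or whether the stated 80% power applies.

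What is at stake depends on the meaning of II.B. If it is the trial total, a null result for 80 mg versus placebo, or for 80 mg versus 20 mg, could be taken as evidence of no blunting from a trial believed to have 80% power when it had less. If it is one site's share, the harm is limited to unlabelled and mismatched figures.

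**Working it through.** **Inputs.** From II.B: cap 80, completers 60 (20 per group). From II.C: 35 per group, d = 0.75, two-sided alpha 0.025, two-sample t-test, 105 final, 120 enrolled, 10% dropout, two equal sites, d = 0.9 from the earlier study, detectable difference 1.53 ml/kg/min.

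**Formula.** Exact t-test power: noncentral t with df = 2n - 2 and noncentrality d x sqrt(n/2), against the critical value t(0.9875, df).

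**Step 1: reproduce II.C.** With n = 35 and d = 0.75, the noncentrality is 0.75 x sqrt(17.5) = 3.14 on 68 df, and power is 79.9%. This agrees with the stated 80%. For dropout, 105/0.9 = 117, so 120 is a reasonable rounding. II.C is internally sound.

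**Step 2: II.B as the trial total.** A cap of 80 is below 105, so II.C's final number is unreachable. The number analysed for week-12 VO2peak could be 20 per group (only the 60 completers), 24 per group (80 x 0.9 = 72, divided by 3) or 26-27 per group (all 80).

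| n per group | Power, d = 0.75 | Power, d = 0.9 | Detectable d at 80% power |
|---|---|---|---|
| 20 | 52% | 70% | 1.01 |
| 24 | 61% | 79% | 0.92 |
| 26-27 | 65-67% | 82-84% | 0.86-0.88 |
| 35 (II.C) | 80% | 93% | 0.75 |

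**Step 3: the SD matters.** II.C implies two different SDs: 1.53/0.75 = 2.04, and (2.6 - 0.4)/0.9 = 2.44. The detectable difference at 20 per group is 1.01 x 2.04 = 2.06 ml/kg/min with the first and 1.01 x 2.44, about 2.47, with the second. At 26-27 per group it is 1.75-1.79 or 2.10-2.14. With SD 2.04, the full earlier difference of 2.2 corresponds to d = 2.2/2.04 = 1.08, and power at 20 per group is then 85%.

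**Step 4: II.B as the KUMC share.** II.C split equally gives 120/2 = 60 enrolled per site, or 20 per group per site. After 10% loss that leaves 54 (18 per group); half of 105 is 52.5. II.B's 60 are people who complete, out of up to 80 randomised. Doubling II.B gives up to 160 randomised and 120 completers, against II.C's 120 and 105. Power is not lost: 40 completers per group give 85.5% (d = 0.75) and 95.7% (d = 0.9). The enrolment and completion figures still do not match.

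**The case against.** The best defence is that II.B is KUMC's share. II.C's 120, split over two sites and three arms, gives II.B's 60 and 20. The document is a KUMC protocol with KUMC recruitment, IRB and pharmacy, and ECU has its own investigator and study physician. This reading is plausible, and on it the power claim survives. It does not make the numbers agree (step 4). II.B's description of 60 as an overall goal and II.G's single location also point the other way.

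A reader might infer that the trial simply has 52% power. The documents do not support that. It needs the trial-total reading, the smaller effect size and the smallest analysed number together. II.B's 60 are completers of all procedures, a set that includes repeat biopsies ("Muscle biopsies will be repeated at 4 weeks and 12 weeks"). More participants than that may provide a week-12 VO2peak, and the mixed model in V.A does not require complete data. Its adjustment for baseline and age may also help, but by how much cannot be computed: the documents give no correlation and do not say whether d is standardised by the SD of change or of the final value.

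A reader might also infer a planned 25% attrition from 60 of 80. Since 80 is a maximum, that ratio bounds the tolerated loss and does not predict it. Nor is it right that every figure lacks a scope: II.C's 120 is the two-site total, and only II.B's figures are unlabelled.

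**Conclusion.** Wrong as written. II.B and II.C disagree on the number randomised, the number finishing and the number per group, and no text reconciles them. This holds on either reading.

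The loss of power is conditional. If II.B is the trial total, the unadjusted test specified in II.C has 52% to 67% power for d = 0.75 instead of 80%. For d = 0.9 it has 70% to 84% instead of 93%. For the full 2.2 ml/kg/min difference with SD 2.04, it has 85% even at 20 per group. If II.B is the KUMC share, there is no loss of power and the fault is one of labelling and mismatch. The documents do not establish which is meant, so the firm conclusion is the inconsistency, not underpowering.

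**What to change.** State one trial-wide enrolment, one analysed number and one attrition rate, identical in II.B and II.C, and label II.B's figures as overall or KUMC. Then, according to what was intended:

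- **80/60 is the trial total:** remove the 120, 105, 40 and 35 figures. Restate the power and detectable difference for the number expected to provide a week-12 VO2peak, naming the SD used.
- **80/60 is the KUMC target:** label it so, say whether 60 means enrolled or completing, and give the other site's target so that the two add up to the II.C total.
- **II.C governs and II.B was meant as trial-wide:** correct II.B's 80, 60 and 20, and the 150 screened, to match II.C. At II.B's own screening ratio, 120 enrolled would need about 120 x 150/80 = 225 screened.

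In every case, reconcile II.G's single location with the two sites in II.C.

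The cost is wording only. In the first case the stated power becomes less favourable. In the third, II.B's figures rise, but to no more participants than II.C already plans.

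### Holm's procedure would give the two primary comparisons more power than the planned single-step Bonferroni rule, at the same familywise 0.05 and with no added participants

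*Combined protocol and SAP*

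**What the plan says.** Section II.C names two VO₂peak contrasts on which the study is powered, both assessed at week 12: "between the EX+Plac group and the EX+Atorva80 group as well as between the EX+Atorva20 group and the EX+Atorva80 group". The power statement reads "A sample size of 35 per group provides 80% of power of detecting an effect size of 0.75". The test behind it is the two-sample t-test, two-sided, with alpha set to 0.025. The level follows from the multiplicity rule: "Here, we use 0.025 for each group comparison to maintain the overall type I error rate at 0.05 level using Bonferroni correction".

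The VO₂peak gain on 20 mg is expected "to be similar to that of EX+Plac group", so the two contrasts against 80 mg have the same assumed effect. From the prior study the section also reports: "The estimated effect size of between group differences is 0.9". The 20 mg versus placebo comparison is exploratory and lies outside the two-test family.

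Section V.A describes a mixed model adjusted for baseline and age. It names no multiplicity procedure, so II.C holds the only rule. No section gives the power for both comparisons together.

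**The concern.** Single-step Bonferroni holds the second test at 0.025 even after the first has been rejected. Holm tests the smaller p-value at 0.025 and, if that is significant, the larger at 0.05. It controls familywise error at 0.05 under any dependence, and every Bonferroni rejection is also a Holm rejection. The plan therefore gives up power without gaining error control.

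The loss is greatest for the two comparisons taken together. Section V.B expects findings that would indicate that "higher dose atorvastatin impair exercise adaptations and that physicians should consider prescribing lower dose atorvastatin to patients". The first half of that message draws on 80 mg versus placebo and the second on 20 mg versus 80 mg. A reader interested in both has no power figure to go by.

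**Working it through.** **Inputs.** From II.C: 35 per arm, d = 0.75, two-sided two-sample t-tests, 0.025 each, 1:1:1 allocation, and 20 mg assumed equal to placebo, so d = 0.75 in both contrasts. For sensitivity: d = 0.9 and 40 enrolled per arm (II.C), and 20 completers per arm (II.B).

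**1. The plan's own figure.** Noncentrality = d·√(n/2) = 0.75 × √17.5 = 3.137, with 68 degrees of freedom. The noncentral t gives power of 79.9% at 0.025, which reproduces the stated 80%. At 0.05 it is 87.1%.

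**2. Dependence.** Both differences use the 80 mg mean. With equal arms each has variance 2σ²/n and their covariance is σ²/n, so the correlation is 0.5.

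**3. Rejection rules for both comparisons.** Bonferroni: larger p < 0.025. Holm: smaller p < 0.025 and larger p < 0.05.

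**4. Simulation** (400,000 three-arm trials, shared 80 mg arm, 35 per arm; d = 0.75 in both contrasts for the power rows):

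| Quantity | Bonferroni | Holm |
|---|---|---|
| A given comparison significant | 79.9% | 84.7% |
| Both significant | 68.5% | 78.1% |
| At least one significant | 91.3% | 91.3% |
| Familywise error, both nulls true | 4.6% | 4.6% |
| Familywise error, one null true and the other effect very large | 2.5% | 5.0% |

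**5. Checks.**
- P(both) + P(at least one) equals the sum of the two single powers. Bonferroni: 2 × 79.9 − 91.3 = 68.5. Holm: (78.1 + 91.3)/2 = 84.7.
- Bivariate normal with correlation 0.5, calibrated to exactly 80% per test: λ = 2.241 + 0.842 = 3.083. Bonferroni joint power = Φ₂(λ − 2.241, λ − 2.241) = 68.7%. Holm joint power = 2Φ₂(λ − 2.241, λ − 1.960) − Φ₂(λ − 2.241, λ − 2.241) = 77.8%.
- With a standard deviation pooled over three arms: 69.4% and 78.6%.

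**6. Sensitivity of joint power:**

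| Per arm | d | Bonferroni | Holm | Gain (points) |
|---|---|---|---|---|
| 35 | 0.75 | 68.5% | 78.1% | 9.6 |
| 35 | 0.9 | 87.5% | 92.6% | 5.1 |
| 40 | 0.75 | 76.6% | 84.5% | 7.9 |
| 20 | 0.75 | 35.5% | 46.6% | 11.1 |
| 20 | 0.9 | 55.0% | 66.3% | 11.3 |

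**7. Equivalent in participants.** Bonferroni needs about 42 per arm to reach about 79% joint power, which is 3 × (42 − 35) = 21 more completers.

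**8. If success requires both.** Testing each comparison at an unadjusted 0.05 and claiming only when both are significant gives joint power of 78.9%.

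**The case against.** The strongest objection is that the plan contains no error. Its 80% is tied to a single t-test at 0.025 and is right, and Bonferroni is a legitimate choice. That stands, and it limits the point to an improvement.

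A reader might infer that the trial has 69% power where it claims 80%, because its conclusion needs both comparisons. The documents do not support this. II.C never claims 80% for both and sets no both-must-win rule. The V.B sentence comes after a long list of expected results on fitness, mitochondrial measures, insulin sensitivity and pain, and is narrative rather than a success criterion. The exploratory non-inferiority assessment of 20 mg against placebo also bears on the low-dose message.

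A second objection is that, if both results were truly required, no adjustment would be needed: each test could be run at 0.05, with joint power slightly above Holm's. That is correct. But splitting alpha implies that the sponsor wants each comparison to be claimable alone. Holm fits that aim, and power for a given comparison still rises by about 5 points.

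Third, the figures are for t-tests, while V.A plans a baseline-adjusted mixed model, and the documents do not say on which scale d is defined. If d refers to unadjusted post-training values and baseline correlates 0.5 with outcome (an assumption), the effective d is 0.75/√(1 − 0.25) = 0.87 and Bonferroni joint power is about 84%. On this point it ranges from 68.5% with no covariate gain to about 84%. The size of Holm's advantage changes; its direction does not.

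Finally, the conflict between 20 completers per arm in II.B and 35 in II.C matters more than the choice of procedure. That is true, and it needs separate reconciliation.

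**Conclusion.** The point holds as a cheap improvement. The planned rule is valid and its stated power is correct per comparison, but Holm is uniformly more powerful at the same familywise 0.05. At 35 per arm and d = 0.75 in both contrasts, the gain is about 5 points for a given comparison (80% to 85%) and 9 to 10 points for both together (68–69% to 78%). The chance of at least one significant result is unchanged at 91%.

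These sizes rest on 35 completers per arm, equal effects in the two contrasts and t-tests. Holm's joint power of 78% still falls just short of 80%. That Holm rejects at least as often as Bonferroni, at the same familywise level, rests on none of these assumptions.

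**What to change.** - In II.C, replace Bonferroni with Holm: the smaller of the two p-values is tested at 0.025 and, if significant, the larger at 0.05.
- In V.A, apply the same rule to the two 12-week primary contrasts from the mixed model. Name those contrasts there, since V.A lists months 0, 1, 6 and 12 and no multiplicity rule. State whether they are tested directly or only after the treatment-by-time test.
- Keep the sample size. State that 35 per arm gives 80% power per comparison at 0.025, and about 78% for both under Holm (about 68–69% under Bonferroni).
- If the sponsor would claim success only when both comparisons are significant, say so instead and test each at 0.05 without adjustment (joint power about 79%).
- Settle the rule before anyone involved sees unblinded data; IV.A plans unblinding after one year.

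The cost is a few sentences in two sections and no participants. One small downside should be disclosed: if simple 97.5% simultaneous intervals are reported, the second comparison can be significant under Holm while its interval includes zero.
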